### 7.2 PARTICIPANT DISCONTINUATION/WITHDRAWAL FROM THE STUDY

Participants are free to withdraw from participation in the study at any time upon request. The reason for participant discontinuation or withdrawal from the study will be recorded on a dropout form, and the patient will be presented with an Informed Consent Form Addendum. With the patient's consent, we will monitor their surgical outcomes through collection of follow-up data from their medical provider and medical record.

Patients who sign the informed consent form and are randomized but do not receive the study intervention may not be replaced and will be included in the intent to treat analysis. Patients who sign the informed consent form, and are randomized and receive the study intervention, and subsequently withdraw, or are withdrawn or discontinued from the study, will not be replaced and will be included in the primary analysis.

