### 9.3 POPULATIONS FOR ANALYSES

Our analysis will adhere strictly to the intent-to-treat principle. All participants randomized will be analyzed according to their allocation.

**Missing Outcomes:** We distinguish two kinds of missing data: missing data in covariates, and missing data for outcomes. For the latter, we distinguish simple loss to follow-up (as when a patient has needed to move out of the area) from data missing because of the occurrence of a medical event (such as the loss of an eye). We will always report the results of complete case analysis, although such results are known to be biased. In the event of missing baseline covariates among >10% of patients, we will use regression based multiple imputation (with at least 100 replicates) to impute these missing covariates (based only on other variables available at baseline). To compare with the complete case analysis, we will also report multiple-imputation based analysis for missing outcomes (or equivalently, likelihood methods which integrate over the missing outcome data based on the same assumption of missingness at random); such analyses are important to report because of the intent to treat principle. Finally, we conduct sensitivity analyses in which the data are not assumed missing at random, to assess how extreme the missing values would need to be to change the conclusions of the study. We propose use of the R package mice (Multiple Imputation by Chained Equations) for multiple imputation; other choices are available and would serve equally well.

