6.2. Analysis methods

Primary Outcome

Visual Acuity at 6 months. We will use a multiple linear regression model to estimate the mean difference between groups in BSCVA measured in logMAR at 6 months. The model will include covariates for treatment arm (a binary indicator variable for RB-PDT), indicators for study site (randomization strata), and baseline pinhole visual acuity. We propose a two-sided alpha of 0.05 for the primary analysis.

For study participants who experience perforation or the need for TPK this will be noted and BSCVA will be recorded prior to performing surgery (either corneal glue or TPK). These study participants actual 6-month visual acuity will be used in the primary analysis. As a sensitivity analysis, the last observation (at 3 weeks or 3 months) will be carried forward (LOCF) as the 6-month BSCVA.

The measurement window for the 6-month primary BSCVA outcome will be 5-9 months. The window was chosen after examining the distribution of measurement timing in masked data. As a sensitivity analysis, we will include all participants, including those who had their primary outcome measured out-of-window.

A supplementary analysis using linear mixed effects regression will be conducted to analyze all BSCVA data (including 3-week and 3-month observations). The model will include baseline BSCVA and treatment assignment as covariates (fixed effects) plus a random effect for patient to allow for repeated measures over time. Such analyses will be sharply distinguished from the primary pre-specified analysis. Permutation testing will be the basis of inference. Specifically, we will conduct 10,000 random permutations of treatment assignment, and conduct the primary regression analysis on these re-randomized data sets. We will then compare the observed regression coefficients to the randomization distribution, reporting the quantiles.

In all analyses, model adequacy will be checked by examination of residuals or other goodness of fit tests as needed. Inadequate model fit will prompt us to report alternative models. If there are chance imbalances in prognostic baseline patient characteristics, a secondary analysis will include them as covariates in the regression model.

Secondary Outcomes

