6.3. Missing data

If outcome data are missing for >15% of participants we will report results from sensitivity analyses for missing data [4,5]. We selected 15% missing because trials with >20% missing values are thought to be a concern for bias [6]. The primary analysis will assume outcomes are

missing completely at random. We will relax this assumption slightly, assuming that outcomes are missing at random (MAR) with an inverse-probability weighted (IPW) estimator. We will model the probability of censoring as a function of baseline patient characteristics with a logistic regression model, and will use the inverse of the predicted probabilities from the model to re-weight the analysis population to reflect the full study population at the time of enrollment, using a doubly-robust targeted maximum likelihood estimator that also includes an outcome model using the same covariates [7]. Baseline characteristics used in the censoring model will include treatment arm, site, age, sex, occupation, medication use at enrollment, eye trauma, ocular measures at enrollment (infiltrate and/or scar size, depth, epithelial defect size, duration of symptoms, BSCVA). We will additionally consider a range of scenarios assuming the outcomes are missing not at random (MNAR), *i.e.* systematically, using a pattern mixture model approach described by Little et al. [4], whereby we model BSCVA with a linear model as a function of covariates listed for the IPW estimator; missing outcomes will then be imputed using the model fit to predict, adding a shift parameter, Δ , that we vary across a range of values.

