7	2024-12-03	
Primary analysis will not do LOCF for CP/TPK but instead use actual 6-month value (Section 6.2). Specified analyses for secondary outcomes (Section 6.2).

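### The REAGIR primary analysis has no value for a perforated or transplanted eye without an in-window acuity, although the protocol says treated participants who withdraw are in the primary analysis

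*SAP*

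**What the plan says.** SAP 6.2 makes the primary analysis a linear regression of 6-month BSCVA on arm, site and baseline pinhole acuity, with a 5-9 month outcome window. For perforation or TPK it says: "These study participants actual 6-month visual acuity will be used in the primary analysis". It continues: "As a sensitivity analysis, the last observation (at 3 weeks or 3 months) will be carried forward (LOCF) as the 6-month BSCVA". The SAP revision history dates this switch to version 7 (2024-12-03).

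SAP 6.3 describes primary outcomes as "missing completely at random. We will relax this assumption slightly". The analyses that relax the assumption are conditional: "If outcome data are missing for >15% of participants we will report results from sensitivity analyses for missing data". Their censoring model lists baseline variables only.

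The protocol differs in three places:
- Section 9.4.1 carries the 3-week or 3-month acuity forward in the primary analysis after perforation or TPK, and makes actual 6-month acuity a separate secondary analysis.
- Section 7.2 says that participants who are treated and then withdraw "will not be replaced and will be included in the primary analysis".
- Section 9.3 says "We will always report the results of complete case analysis, although such results are known to be biased". It separates simple loss to follow-up from data missing because of a medical event. It also promises multiple imputation of missing outcomes and not-at-random sensitivity analyses, with no percentage trigger.

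SAP 3.2, 3.4 and 4.2 describe an intention-to-treat analysis of everyone randomized.

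**The concern.** A failed eye that returns in the window stays in the primary comparison. One that does not return has no value there. Under the protocol rule the same eye would keep its 3-week or 3-month acuity where one exists. The SAP moved that rule to a sensitivity analysis and put nothing in its place.

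Such missingness is unlikely to be MCAR. Perforation and TPK happen after randomization and go with poor vision, and SAP 2.2 anticipates that their rate differs by arm. Nothing in the primary model captures them. If failed eyes return less often than others, the regression estimates a difference among those who returned, and not the difference among all randomized.

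Both directions matter. The hypothesis is fewer failures with RB-PDT. Protocol 2.2 also reports a small trial of cross-linking in deep fungal ulcers that stopped over concern about perforation.

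**Working it through.** **1. The plan's own figures reproduce.** Inputs are from SAP 3.3. Residual SD = 0.293 × √(1 − 0.216²) = 0.286. Evaluable per arm = 165 × 0.85 ≈ 140. Planned SE = 0.286 × √(2/140) = 0.034. The detectable difference at two-sided 0.05 is (1.960 + 1.282) × 0.0342 = 0.111 at 90% power and (1.960 + 0.842) × 0.0342 = 0.096 at 80%. These match the stated 0.11 and 0.10.

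**2. The missing-data trigger.** 15% of 330 is 49.5, so the analyses in SAP 6.3 start at 50 missing outcomes. The design allows for about 15% loss. Loss at or just under the planned level triggers none of them.

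**3. Size of the bias.** The documents give no return rates by event status, so the following are assumptions:
- p is the perforation/TPK rate in an arm (S sham, R RB-PDT), and p̄ is the mean of the two rates.
- mE is the loss in failed eyes, the same in both arms. mN is the loss in other eyes, set so that p̄·mE + (1 − p̄)·mN = 0.15.
- g is how much worse failed eyes see, in logMAR.

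Observed share of failed eyes: q = p(1 − mE) / [p(1 − mE) + (1 − p)(1 − mN)].
Bias in RB-PDT minus sham = g × [(qR − pR) − (qS − pS)]. The effect due to failures is g × (pR − pS); positive means worse vision on RB-PDT.

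Example with pS 0.30, pR 0.15, mE 0.30, g 0.8:
- mN = (0.15 − 0.225 × 0.30)/0.775 = 0.1065
- qS = 0.210/(0.210 + 0.70 × 0.8935) = 0.2514
- qR = 0.105/(0.105 + 0.85 × 0.8935) = 0.1215
- Bias = 0.8 × [(0.1215 − 0.15) − (0.2514 − 0.30)] = 0.016

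The same steps with mE 0.30 and g 0.8 give:

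| Sham v RB-PDT rate | Effect | Complete-case | Bias | % of effect | % of 0.11 | Bias/SE |
|---|---|---|---|---|---|---|
| 20% v 10% | −0.080 | −0.068 | 0.012 | 15 | 11 | 0.35 |
| 30% v 15% | −0.120 | −0.104 | 0.016 | 13 | 15 | 0.47 |
| 50% v 25% | −0.200 | −0.182 | 0.018 | 9 | 16 | 0.52 |
| 10% v 20% | +0.080 | +0.068 | −0.012 | 15 | 11 | 0.35 |

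The 50% is the approximate rate that Protocol 2.2 gives for an earlier fungal trial.

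**4. Range.** Across gaps of 0.5-1.0 and rates of 20/10, 30/15 and 40/20, the bias is about 2-6% of 0.11 with 20% loss in failed eyes and about 12-37% with 40% loss. At 50% v 40% with 20-30% loss it is about 1-5%. If failed eyes return more often than others, the sign reverses: at 30/15 with mE 0.10, mN = (0.15 − 0.0225)/0.775 = 0.1645, and bias = 0.8 × [(0.1597 − 0.15) − (0.3158 − 0.30)] = −0.005.

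**5. If return after failure also differs by arm.** This is a separate assumption: equal failure rates of 30% or 50%, all other eyes return, gap 0.5-1.0. Non-return of failed eyes of 20% v 30%, 10% v 30% or 20% v 40% (sham v RB-PDT) shifts the estimate by 0.012-0.069 in favour of RB-PDT, with total missingness of 6-15%. Nothing in the documents suggests such a difference, and patients and treating physicians are masked.

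**The case against.** **The driving assumption is undocumented.** No passage says that failed eyes return less often. Protocol 5.5 expects high retention, and Protocol 7.2 adds a consent addendum to collect follow-up data after dropout. This stands, and it is why the sign is unknown.

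**The larger scenarios strain the plan's variance.** A 0.8 gap alone gives an SD of 0.8 × √(0.225 × 0.775) = 0.33 at a mean rate of 22.5%, and 0.8 × √(0.375 × 0.625) = 0.39 at 37.5%, against a planned total of 0.293. This also stands; those rows show order of magnitude only.

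**Safeguards exist.** SAP 6.2 has an unconditional LOCF sensitivity analysis, an out-of-window analysis and a mixed model using 3-week and 3-month acuity. Protocol 9.3 promises multiple imputation beside the complete-case result. All help interpretation, but none is the primary estimate. The SAP 6.3 analyses, even if triggered, cannot use perforation or TPK status, because their censoring model is baseline-only.

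**Protocol 7.2 may only state allocation.** It prescribes no imputation, and Protocol 9.3 always reports complete case, so a complete-case result is not forbidden. That is fair. But a participant with no outcome value is not included in a regression in any useful sense, and Protocol 9.3 itself calls the result biased.

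**What a reader might infer about harm.** A reader might infer that the primary result could hide visual harm. The arithmetic does not support this where loss depends on failure and not on arm: an effect of +0.080 becomes +0.068, with the same sign. Perforation/TPK is also analysed by a Cox model (SAP 6.2), and the DSMC reviews perforation (SAP 3.5).

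**Conclusion.** The gap is real. That failed eyes without an in-window value drop out is inferred from a regression on 6-month acuity, the MCAR statement and the absence of any substitute value; the SAP does not use the term complete case. It conflicts with Protocol 7.2 on its plain reading, with the intention-to-treat statements and with Protocol 9.3. The LOCF rule in Protocol 9.4.1 and the actual-value rule in SAP 6.2 also contradict each other.

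The likely consequence is modest: 0.012-0.018 logMAR in the main scenarios, a dilution of about 9-15% of the assumed effect. It could reach about 37% of 0.11 at 40% loss in failed eyes, and it reverses if failed eyes return more often. All of this rests on assumed failure, return and acuity figures.

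A reader might also infer that version 7 brought in the MCAR assumption. The revision history ties only the LOCF change, and the specification of secondary analyses, to that version; it does not record when the MCAR wording entered. Nor did the carry-forward rule cover every failed eye: one with neither a 3-week nor a 3-month acuity has no value under Protocol 9.4.1 either.

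The point should be corrected, because the remedy is cheap and delivers what the protocol already promises.

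**What to change.** Amend SAP 6.2 and 6.3 before unmasking:
- Keep the actual 6-month BSCVA wherever it was measured in the window.
- Multiply impute missing 6-month BSCVA by arm, with the mice package named in Protocol 9.3. Use site, baseline acuity, 3-week and 3-month BSCVA, perforation/TPK status and the pre-surgery BSCVA that SAP 6.2 already records.
- Fit the SAP 6.2 regression to each imputed data set, pool, and make this the primary estimate.
- State the number of imputations in the SAP, for example 100. The figure of at least 100 in Protocol 9.3 is for missing baseline covariates and does not settle this.
- Report the complete-case and LOCF analyses as sensitivity analyses, and run the delta-shift not-at-random analysis whatever the percentage missing.
- Reconcile Protocol 7.2 and 9.4.1 with SAP 6.2.

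No new data are needed. The assumption becomes missing at random given post-baseline acuity and event status, which is weaker than MCAR and so a gain. The costs are some programming, reliance on an imputation model, and another change of primary estimator after version 7 in a trial with a planned unmasked interim analysis. Masked staff should therefore make the change, and the revision history should date it and state its timing relative to the interim analysis.

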## 9.4 STATISTICAL ANALYSES

### 9.4.1 ANALYSIS OF THE PRIMARY EFFICACY ENDPOINT

The **Statistical Analysis Plans** for SCUT II, REAGIR, and REAGIR II include more detail about planned analyses. The primary outcome will be 6-month BSCVA, and the primary analysis of each trial will use the same approach. We will use multiple linear regression models to evaluate BSCVA measured at 6 months with covariates for treatment arm (expressed as a binary indicator variable for steroids and a binary indicator variable for cross-linking), indicators for study site (randomization strata), and BSCVA measured on Day 1 (before treatment). We propose a two-sided alpha of 0.025 for each pairwise primary comparison. Specifically, we propose to contrast Groups 1 and 2 using a linear model in which we use baseline visual acuity and a binary indicator for assignment to Group 2 as predictors, and BSCVA as the outcome variable. We then propose to contrast Groups 2 and 3 separately using a model with baseline visual acuity and a binary indicator for assignment to Group 3 as predictors, with BSCVA as the outcome variable.

For study participants who experience perforation or the need for TPK this will be noted and BSCVA will be recorded prior to performing surgery (either corneal glue or TPK). The last observation (at 3 weeks or 3 months) will be carried forward (LOCF) as the 6-month BSCVA, but a separate secondary analysis will include these study participants actual 6-month visual acuity.

A supplementary analysis using linear mixed effects regression will be conducted to analyze all BSCVA data (including 3-week and 3-month observations). The model will include baseline BSCVA and treatment assignment as covariates (fixed effects) plus a random effect for patient to allow for repeated measures over time. Such analyses will be sharply distinguished from the primary pre-specified analysis. Permutation testing will be the basis of inference. Specifically, we will conduct 10,000 random permutations of treatment assignment, and conduct the primary regression analysis on these re-

randomized data sets. We will then compare the observed regression coefficients to the randomization distribution, reporting the quantiles.

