3.2. Randomization

Randomization will be stratified by site. Stratified, block randomization will ensure that an approximately equal number of patients are randomized to each treatment group by site. The exact block size will be randomly permuted (e.g., block size of 4 with probability 0.7 and 6 with probability 0.3) with block sizes and their probabilities known only to the biostatistician.

Once an eye is in the study enrolled (only one eye can be enrolled from each patient), the study coordinator will assign the study participant's eye an ID (alpha-numeric code) and organize the procedure in the operating room within 48 hours of enrollment. Once the study participant has been assigned a study participant ID and randomized to treatment arm, they will be included in the intent to treat analysis.

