6.4. Additional analyses

We plan to complete the following exploratory analyses.

Imaging Outcomes. To be analyzed by a **masked grader** in the **Proctor Reading Center (PRC)**. We propose five different analyses, based on imaging at baseline, 3 weeks, 3 months, 6 months and 12 months.

- **Confocal Microscopy.** An *in vivo* microscope, which allows examination of the cornea at the cellular level. Outcomes include quantitative estimates of the infectious organism (if visualized on confocal), basal nerve plexus density, white blood cell and keratocyte density in the cornea (these are continuous outcome variables). (based on the Heidelberg Retina Romograph II, Rostock Cornea Module (RCM; Heidelberg Engineering, GmbH, Germany).
 - **Corneal nerves:** Will be analyzed with *ACCMetrics*, an automated corneal nerve fiber analyzer with output variables such as corneal nerve fiber density, branch density, fiber length.
 - **White blood cell/keratocyte density:** Manual quantitative analysis of epithelial cells, inflammatory cells and keratocytes will be performed by a masked grader at the PRC. Stromal depth for the demarcation line and RB-PDT-induced photo-oxidative damage will also be assessed.
 - **Statistical analysis:** We propose to conduct linear mixed effects regression using treatment assignment and baseline values as covariates, using the same template as we did for BSCVA. The most important analysis will be for contrasting the RB-PDT versus RB-PDT sham groups, though we will also examine the effects of steroids. We note that changes over time are possible, and so an interaction with time will be included. This is a secondary analysis.
- **Pentacam Scheimpflug Tomography.** Is a rotating scheimpflug camera, which provides 3 dimensional images of the cornea. In addition to topographic maps with keratometric readings of the anterior and posterior cornea, Pentacam reports on the total corneal power, corneal thickness maps, higher order aberrations and densitometry.
 - **Astigmatism:** comparing steep and flat Ks and total astigmatism in diopters between groups controlling for baseline measurements
 - **Higher order aberrations:** comparing the quantitative measure of irregular astigmatism, expressed in microns as the root mean square (RMS) of the

- Zernike polynomials across the pupil (approximately central 4 mm of the pupil) controlling for baseline measurements

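### The supplementary BSCVA mixed model has no visit, visit-by-treatment or site term, so it estimates a visit-averaged effect that equals the 6-month effect only if the effect is constant

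*SAP*

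**What the plan says.** SAP 6.2, after the primary regression: "A supplementary analysis using linear mixed effects regression will be conducted to analyze all BSCVA data (including 3-week and 3-month observations". The terms follow: "The model will include baseline BSCVA and treatment assignment as covariates (fixed effects) plus a random effect for patient", the random effect being there for repeated measures. Protocol 9.4.1 has the same model: "A supplementary analysis using linear mixed effects regression will be conducted to analyze all BSCVA data", with the same terms. Neither document says whether the 12-month visit enters.

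Three other places bear on this.

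- **Site.** SAP 3.2: "Randomization will be stratified by site". The primary model in SAP 6.2 includes "indicators for study site (randomization strata), and baseline pinhole visual acuity". The mixed model lists no site term, and its baseline covariate is BSCVA, not pinhole acuity.
- **Time.** For the confocal mixed model, SAP 6.4 says that "changes over time are possible, and so an interaction with time will be included". SAP 6.2 has no such sentence for acuity.
- **Status.** SAP 6.2 calls the model supplementary and adds: "Such analyses will be sharply distinguished from the primary pre-specified analysis".

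**The concern.** The trial's question is acuity at 6 months. A repeated-measures model is usually read beside the 6-month regression as a check that also uses the earlier visits. With a single treatment coefficient and no visit interaction, this one estimates a different quantity: the effect averaged over whichever visits are observed. If benefit builds up during healing, the coefficient understates the 6-month effect and may appear to contradict a positive primary result. If an early benefit fades, it may appear to corroborate a 6-month benefit that is not there.

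Two smaller matters go with this. Leaving out site ignores the randomization stratum and puts between-site differences into the error. Leaving out the visit main effect lets any overall trend in acuity enter the treatment comparison when the arms differ in which visits they miss.

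**Working it through.** **Inputs from the documents (SAP 3.3).** SD 0.293 logMAR; correlation with baseline 0.216; 165 per arm; 15% loss; two-sided alpha 0.05; effect 0.11.

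**Inputs assumed.** Effect at each visit, within-patient correlation ρ, trend in mean acuity, missingness by visit and arm, and size of site differences. The documents give none of these for a repeated-measures model.

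**1. The plan's own figure.** Residual SD = 0.293 × √(1 − 0.216²) = 0.2861. Evaluable per arm = 165 × 0.85 ≈ 140. Standard error = 0.2861 × √(2/140) = 0.0342. Power = Φ(0.11/0.0342 − 1.96) = 0.896, which matches the stated 90%. This calculation concerns the 6-month regression, and the point raised here does not alter it.

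**2. What the mixed model estimates.** With m balanced visits and a random intercept, the coefficient is the plain mean of the visit-specific effects. The SD of a patient's average is 0.2861 × √((1 + (m − 1)ρ)/m). With m = 3, 140 per arm, and ρ = 0.3, 0.5 and 0.7:

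| Assumed effect at 3 wk, 3 mo, 6 mo | 6-month effect | Mixed model targets | Power of mixed model | Power at 6 months |
|---|---|---|---|---|
| 0.11, 0.11, 0.11 | 0.11 | 0.11 | 0.99, 0.98, 0.95 | 0.896 |
| 0, 0.055, 0.11 | 0.11 | 0.055 | 0.60, 0.50, 0.44 | 0.896 |
| 0.11, 0.055, 0 | 0 | 0.055 | 0.60, 0.50, 0.44 | 0.025 in the benefit direction |

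The second and third rows have the same coefficient and opposite 6-month truths. Simulation (140 per arm, ρ = 0.5, 60 replicates, benefit coded negative) agrees. The model as written gave −0.055 and −0.058. With visit and visit-by-treatment added, the 6-month estimates were −0.105 (true −0.11) and −0.007 (true 0), with a Monte Carlo standard error of about 0.004.

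The 12-month question matters too. If that visit enters and the second profile stays at 0.11, the target becomes (0 + 0.055 + 0.11 + 0.11)/4 = 0.069.

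**3. A milder profile.** With effects 0.02, 0.07 and 0.11, the plain mean is 0.20/3 = 0.067. Weighting by attendance of 97%, 92% and 85% gives (0.0194 + 0.0644 + 0.0935)/2.74 = 0.065. Simulation gave 0.065 as written and 0.111 for the 6-month contrast; other runs under similar assumptions gave 0.063 to 0.067 and 0.111 to 0.115.

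**4. Precision.** Adding visit and site main effects lowered the model standard error from 0.030 to 0.028 in simulation. In the step 2 runs, with complete visits and no site differences, the model as written already had a standard error of about 0.028. The gain therefore comes mainly from site, and its size depends on the site differences assumed.

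The 6-month contrast costs precision in return. At ρ = 0.5 with complete data, the averaged effect has standard error 0.2861 × √(2/3) × √(2/140) = 0.028, against 0.034 for the single visit. With missing visits the simulation gave 0.028 and 0.036.

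**5. Missed visits.** Suppose mean acuity runs 0.8, 0.6, 0.5 logMAR over the three visits and treatment does nothing. A patient seen three times averages 0.633; one who misses 6 months averages 0.700. If 6-month loss is 10% in one arm and 20% in the other, the arms differ by roughly 0.10 × 0.067 = 0.007. A 15-point difference gives 0.15 × 0.067 = 0.010. If loss is equal in the two arms, the term cancels.

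Simulations at 10% v 20% gave 0.007 (Monte Carlo standard error 0.003) and, in another run, −0.0025 (0.0026), which is not distinguishable from zero. A further scenario with arm-dependent missingness gave about 0.01, removed by adding the main effects. The bias is small.

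**The case against.** The strongest reply is that the model is supplementary and kept apart from the primary analysis, and that an average over visits is a legitimate quantity. If the effect is constant, the pooled coefficient is unbiased and more powerful than the 6-month comparison (0.95 to 0.99 against 0.896). Readers will also have the primary 6-month regression and, under SAP 6.2, separate regressions at 3 weeks, 3 months and 12 months, so a late or fading effect would not stay hidden. All of this stands. It limits the consequence, but it does not tell the reader what the mixed model estimates, and neither document calls it an average.

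SAP 6.2 also promises alternative models if fit is poor. That is a real safeguard, but it names no alternative and leaves the choice until the data have been seen.

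Four stronger readings are tempting and do not hold.

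- *The model cannot support the 6-month result.* That depends on the effect varying over time. The documents neither assume nor exclude this.
- *Leaving out site causes the averaging.* It does not. Site is a separate mismatch with the stratified design and the primary model.
- *Unequal missingness across visits biases the coefficient.* Unequal loss over time changes the weights in the average. Bias under no effect needs loss that differs by arm.
- *This model is the plan's check under missing at random.* No passage gives it that role. SAP 6.3 plans a weighted, doubly robust analysis and shifted imputation if more than 15% of outcomes are missing, and Protocol 9.3 plans multiple imputation.

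**Conclusion.** The point holds in a limited form. As listed in both documents, the supplementary model gives one visit-averaged treatment effect. Whether that differs from the 6-month effect depends on a profile the documents do not supply: no difference if the effect is constant, about 0.065 against 0.11 under the mild ramp, and half or a spurious 0.055 under the steeper profiles. Omitting the main effects costs a little precision (0.030 against 0.028 in one simulation) and allows a small bias, about 0.01 logMAR, if missed visits differ by arm. These sizes rest on assumed inputs.

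A reader might infer that the trial's main result is at risk. It is not. The primary regression, its alpha, the sample size, the visit-specific regressions and the missing-data analyses are all unaffected.

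**What to change.** In SAP 6.2, and in the matching sentence of Protocol 9.4.1:

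- Add categorical visit and site as fixed effects, and a visit-by-treatment interaction in line with what SAP 6.4 does for confocal imaging.
- Report the 6-month treatment contrast from this model.
- If a pooled coefficient is also reported, label it as the average over visits. Keep visit and site in that version too.
- State whether 12-month data enter and which baseline acuity measure is used. State also which statistic the permutation test applies to: the text re-runs the primary regression, which leaves inference for the mixed model unclear.

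The cost is a wording change, with no new data. It should be made before unmasking. The statistical price falls only on the 6-month contrast: if the effect is constant, its standard error is about 0.036 against 0.028 for the pooled effect (0.036/0.028 = 1.29). That is a reason to show both. Adding the visit and site main effects has no comparable price.
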